Fewer than 50% of individuals with stroke have their risk factors assessed, treated, or controlled. Of those overweight at initial evaluation, 90% remain overweight. Nearly half of hypertensive individuals do not have blood pressure controlled. Smokers do not quit and few participate in exercise programs. At three months post-discharge, only 75% of stroke patients are still taking their preventive medications. About 40% remain dependent on others. Stroke also affects caregivers. Caregivers have poorer mental health, less social contact and activity, and are at increased risk for depression.

Comprehensive post-acute services for stroke require bridging hospital-based acute care with expanded care teams for rehabilitation, primary care management, access to community resources, and caregiver support. Evidence-based reviews have concluded that stroke morbidity and mortality could be reduced through effective transitional care, ^{22–24} secondary prevention, ²⁵ and rehabilitation early post-stroke. ²⁶ Involvement with a stroke liaison worker or case manager is associated with more knowledge about stroke and satisfaction with services. ^{27,28} Caregiver-oriented, individualized discharge planning for stroke patients going home improves caregiver preparedness. ²⁹

Given the significant impact of stroke on public health, the high risk and complexity of these patients early after discharge, and the strain on caregivers, an effective post-acute care model is needed. A pragmatic trial is the ideal method to test a care model that can be readily disseminated and implemented.

Objectives & Specific Aims

The COMprehensive Post-Acute Stroke Services (COMPASS) Study will determine the effectiveness of a post-acute comprehensive intervention.

Primary Study Question:

Does implementation of the COMPASS for stroke patients discharged directly home, improve functional outcomes (measured by the Stroke Impact Scale-16) at 90 days post-stroke? Intention-to-treat principles will be used to determine all primary and secondary outcomes.

Primary Aim:

Comparative effectiveness of COMPASS verses usual care (Control) on stroke survivor functional status (measured by the Stroke Impact Scale) at 90 days post-stroke.

Secondary Aims:

- 1) Using responses from the 90 day caregiver survey, determine if the COMPASS intervention reduces caregiver strain (measured by the Modified Caregiver Strain Index) at 90 days post-stroke.

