This is a community-engaged study. Patients, family caregivers, and others stakeholders will be involved in all phases of the research process. These community members will be engaged in non-research activities (e.g., revising study materials for clarity) as well as research activities (e.g., participating in focus groups). By design, community-engaged research requires decision making by many stakeholders and frequent IRB amendments. For clarity and oversight purposes we have submitted a separate IRB (PCORI Stakeholder Interviews: IRB00028495; Appendix 31) for research activities involving stakeholders.

Phase 1 Only: Implementation Analysis

We will be asking participating staff at implementing sites (approximately 20 PACs and COMPASS team members) to agree to have their responses on the Bi-weekly Implementation Calls and surveys recorded and transcribed and analyzed to better understand the process of implementing the COMPASS Care Model. We will be asking participating staff at implementing sites (approximately 40 therapy care providers and COMPASS team members) to agree to have their responses on the Bi-weekly Home Health and Outpatient Calls and surveys recorded and transcribed and analyzed to

Application - IRB00035998

better understand the process of implementing the COMPASS Care Model. We will also be asking study staff COMPASS Director of Implementation and members of the Implementation Committee for individual semi-structured interviews. Additional detail to this study activity is provided in Appendix 33.

Data Collection and Outcome Measures

Patient Participant Study Outcomes (Phase 1 and 2):

	Measure	Assessment(s)	When Collected	Appendix
Primary Outcome	Physical Function	Stroke Impact Scale (SIS-16)	@90 days, consenting patients asked by CSRL	23
Secondary Outcome	Self-rated General Health	A question rating health on a 5-point scale & a question on perception of health improvement	@90 days, consenting patients asked by CSRL	24
Secondary Outcome	Disability and Dependence	Modified Rankin Scale	@90 days, consenting patients asked by CSRL	24
Secondary Outcome	Physical Activity	Three questions which ask about time spent walking	@90 days, consenting patients asked by CSRL	24
Secondary Outcome	Depression	Patient Health Questionnaire (PHQ-2) Note: these items do not ask about suicidal thoughts or actions	@90 days, consenting patients asked by CSRL	24

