As described above, this pragmatic trial utilizes a cluster randomized design with 41 hospitals being randomized to receive the COMPASS intervention (N=20) or control (N=20) in Phase 1. In Phase 2, the control group hospitals will be rolled into the intervention (Figure 1). All stroke patients who are discharged directly home from one of the randomized hospitals will be included in the intention-to-treat analyses. Analyses will be performed at the individual (patient) level, with adjustments for hospital and/or patient level characteristics to control for possible correlations of patients within hospitals.

We used two stratification factors in randomization: annual stroke patient volume per hospital (3 levels: <100, 100-299, 300+ patients) and whether the hospital is a primary stroke center (Yes/No). Thus, there will be a total of 6 strata. We will use a random permuted block design with block size of two; within each stratum we will randomize an even number of hospitals. This will allow us to maintain balance between the treatment groups while also protecting the validity of the randomization process. Study team involved with site selection will not have access to the randomization schedule which will be held by [name]. Likewise, [name] will not be involved in site selection. Although patients in the intervention cannot be blinded to their group assignment, interviewers gathering outcome data will be blinded. Our estimated sample size will permit pre-specified subgroup analyses by race, gender, age, stroke severity and insurance status.

For the primary aim, the primary endpoint is the Stroke Impact Scale (SIS-16) measured 90 days post-stroke. The secondary aims include the Modified Caregiver Strain Index at 90 days; 30- and 90-day all-cause readmissions; and mortality, health care utilization, continuity of care, utilization of transitional care, and medication adherence, all measured 1 year after index discharge. In addition, analyses by race, gender, age, stroke severity and insurance status will determine if there is evidence of heterogeneity of the intervention effect across any subgroups. Finally, for the two exploratory aims, we will (1) examine hospital-level measures of stroke care quality indicators in the COMPASS hospitals, and (2) compare administrative claims outcomes and post-acute stroke performance outcomes between COMPASS patients in Phase 1 (intervention phase) and Phase 2 (sustainability phase).

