Since the primary endpoint (SIS-16) is measured on a continuous scale, we will use a mixed model to compare the COMPASS and control groups. Although the stratified randomization of hospitals should balance most important hospital-level characteristics between groups, since imbalances may exist between groups on patient-level characteristics, we propose to include both fixed and random effects in this mixed model. The first model will include two fixed effects: stratum (1 to 6) and the intervention effect (COMPASS vs. control) and one random effect: hospital. This additive model can be written as: $Y_{ijk} = \mu + \gamma_k + \alpha_j + \beta_{k(j)} + \epsilon_{i(jk)}$, where Y_{ijk} is the outcome (i.e. SIS at 90 days) measured on the i^{th} patient, under the j^{th} intervention (j=1 (COMPASS), 2(Control) in the k^{th} hospital; μ is the grand mean; γ_k is the stratum (1 to 6) for hospital k; α_j is the fixed treatment effect for group j (COMPASS/CNT); $\beta_{k(j)}$ is the random effect of the k^{th} hospital nested within the exposure group; and $\epsilon_{i(jk)}$ is the error term for the i^{th} patient nested within the treatment group and hospital. Other fixed effects can be added at the patient level (e.g. age, gender, race, stroke severity, or SES) for sensitivity analyses. The random hospital effect allows the possibility of correlated observations (patients) within hospitals. Of primary interest is the treatment effect (α_i), which indicates difference in the dependent variable (SIS-16) between groups.

After we fit our primary model, we will consider other models that may include more patient-level and hospital-level characteristics. For instance, since some patients may be transferred to a different hospital before being discharged home, we can include a yes/no variable on that point. Although hospitals will be stratified pre-randomization based on stroke volume, we can include a hospital-level covariate for the total number of stroke patients discharged home for each hospital. With 40 clusters (of the 41 hospitals, 2 were randomized together) included, we will be able to add other cluster-level covariates to the model if needed.

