Minimal/No Risk Intervention: Participation in the COMPASS study does not expose patients to any additional risks and therefor it is a minimal-risk or no-risk intervention. The COMPASS model and intervention activities are not experimental. COMPASS is evidence-based, and considered best practice for management of post-acute care. CMS supports the delivery of these types of post-acute services and has implemented billing codes (TCM and CCM) to actualize implementation of these services. Hospitals which participate in the COMPASS Study will be asked to implement at the hospital-level these evidence-based services into the systematic delivery of post-acute care to all stroke patients. The COMPASS Study will determine effectiveness of this model on self-reported functional outcomes.

In order to minimize potential differences in loss to follow-up between the control and intervention groups we will send reminder letters (as described in the intervention section) to both control and intervention groups. These letters will include resources from the American Stroke Association (ASA). We will include a refrigerator magnet to remind them that we will call stroke survivors and survey caregivers at 90 days to assess outcomes.

Informed Consent

As a pragmatic trial, our eligibility and outcomes assessment will include all patients discharged home from participating hospitals who are adopting the non-experimental, evidence-based intervention as the new model of care. Our approach has been to minimize patient risk and maximize participation by providing an informational brochure to patients and their families during the hospital stay (or informing by mail), and allow them to opt out of the follow-up phone call at 90 days.

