will be kept confidential and secure and will abide to HIPAA regulations; a reminder that providing consent is voluntary; identification of funding agency, study PI, and institution; contact information should the patient want to withdraw

Application - IRB00035998

(Appendix 21). Patient will use his/her finger to sign and date on the iPad for capture of written signature. (A paper version of the consent form is also available.) The PAC who will be conducting the consent process will also sign and date. A hard copy of consent script will be printed out for the patient to take with them. If the patient declines consent, this will also be noted. In order to not disrupt the clinical work-flow, consent will be collected during the visit either inbetween assessments or at the end of the visit.

Consent for the 90 Day Phone Survey for Patients (All Patients): All stroke patients (or representing proxies) will consent to (or decline) participation in the survey of outcomes. COMPASS will rely on the Full HIPAA Waiver for this phone survey, however we have included in the 80 day reminder letter, information on HIPAA for the patient to make an informed decision on if they would like to participating in the phone survey. Verbal consent at the introduction of the telephone survey should adequately protect the individuals' rights of patient participants. Study-eligible patients are discharged home, and thus proxy support is unlikely to be needed. If the patient prefers a proxy to complete the survey, the patient can ask the proxy to support them in responding. We will record whether the data are provided by the proxy or the patient.

Consent for the 95 Day Paper Survey Mailed to Caregivers (All Caregivers): Caregivers will be asked to respond to a paper survey questionnaire. This questionnaire does not have any questions about the patient, therefore we are not asking for permission from patients to send this survey to caregivers. Response to the questionnaire will be considered consent and HIPAA Authorization to participate in the study.

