6.4 Approaches for Dealing with Missing Data

All analyses performed will make use of data only for COMPASS Study patients who are able to be linked with the claims database.

Data from the COMPASS Study indicate that several important baseline characteristics will be missing for 5-10% of patients.⁴ We will use multiple imputation by chained equations (MICE) to impute missing NIHSS, race, and other potential confounders as necessary. Primary and secondary endpoint analyses will be based on 100 imputed datasets. For each imputed dataset analysis procedures described above will be performed and the parameter estimates will be combined across imputed datasets using standard techniques. More details can be found in the COMPASS Study Phase I Statistical Analysis Plan to which this document is an addendum.

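### As written, the primary SIS-16 model defaults to 90-day survey respondents, with no stated method for missing SIS-16, although intention-to-treat is promised for all patients discharged home

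*Protocol*

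**What the plan says.** **Population.** The primary study question in the protocol's Objectives & Specific Aims states: "Intention-to-treat principles will be used to determine all primary and secondary outcomes". The Analytical Plan adds: "All stroke patients who are discharged directly home from one of the randomized hospitals will be included in the intention-to-treat analyses".

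**Outcome.** The table under Data Collection and Outcome Measures lists SIS-16 as collected at "90 days, consenting patients asked by CSRL", CSRL being the survey laboratory. Under Informed Consent, "All stroke patients (or representing proxies) will consent to (or decline) participation in the survey of outcomes". A patient may ask a proxy to answer. If telephone contact fails, a short paper form containing the SIS-16 is mailed with prepaid return (Phase 1 sections for both arms).

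**Model.** In the Analytical Plan, "The first model will include two fixed effects: stratum (1 to 6) and the intervention effect (COMPASS vs. control) and one random effect: hospital". The outcome term is a single 90-day score per patient. There is no baseline SIS-16 and no repeated measure. Patient-level covariates may be added for sensitivity analyses.

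**Missing data.** Human Subjects Protection says: "In order to minimize potential differences in loss to follow-up between the control and intervention groups we will send reminder letters". The only SAP supplied is the claims addendum. Its section 6.4 says: "We will use multiple imputation by chained equations (MICE) to impute missing NIHSS, race, and other potential confounders as necessary". It does not mention SIS-16 and refers to a separate Phase 1 SAP for more detail.

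**Withdrawals.** Under Appendix 39, a patient who withdraws at any time contributes nothing beyond the eligibility screening form.

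**The concern.** The promised population and the stated model do not meet. A random hospital effect lets patients of one hospital share information about that hospital's level. It recovers nothing for an individual who has no score. With one outcome per patient and no patient covariate, fitting the model as written means fitting it to whoever has a SIS-16 value. Patients who refuse, cannot be reached or die before day 90 drop out without comment.

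This matters most if the reasons for having a score differ by arm. The procedures leave room for that. Intervention patients alone receive the 2-day call, the 7–14 day clinic visit and the 30- and 60-day calls. The 2-day call can collect a caregiver's number (Appendix 16), and the clinic assessment asks for the best number to reach the patient (Appendix 17). The eCare application may update patient data in the COMPASS database, from which the survey laboratory's call list is exported. Contact details could thus be refreshed in one arm only. More contact could also tire patients of being called. Patients are told which arm their hospital is in.

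If response, or its link to outcome, differs by arm, the primary contrast compares two differently selected groups of respondents. With no method fixed in advance, the analysis set and the handling of missing scores remain open to choice after the data are seen.

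**Working it through.** **What the documents give.** Phase 1 has about 6,000 potentially eligible participants (Sample Size) and 40 randomised units (Analytical Plan). Death within 90 days was about 2.0%, with no difference by arm (SAP 6.2). They give no expected response rate, SD, ICC or target difference for SIS-16, so there is no plan figure to reproduce.

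**Formula.** Let r be the proportion responding in an arm and D the mean SIS-16 of respondents minus that of non-respondents. The full mean is the respondent mean minus (1 − r)D. The bias of the respondents-only contrast, COMPASS minus control, is therefore

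(1 − r₁)D₁ − (1 − r₀)D₀.

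**Scenarios.** Every r and D below is an assumption. A negative value runs against COMPASS if a higher score means better function.

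| Response, COMPASS / control | Gap D, COMPASS / control | Calculation | Bias (points) |
|---|---|---|---|
| 60% / 60% | 10 / 10 | 4.0 − 4.0 | 0 |
| 62% / 57% | 8 / 8 | 3.04 − 3.44 | −0.4 |
| 65% / 55% | 10 / 10 | 3.5 − 4.5 | −1.0 |
| 60% / 55% | 8 / 10 | 3.2 − 4.5 | −1.3 |
| 60% / 60% | 6 / 10 | 2.4 − 4.0 | −1.6 |
| 60% / 60% | 12 / 8 | 4.8 − 3.2 | +1.6 |

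Unequal response and unequal gaps can also cancel: 80% / 70% with gaps of 12 / 8 gives 0.20 × 12 − 0.30 × 8 = 0. The table illustrates and does not bound. Setting the extremes of these ranges against each other gives 0.35 × 6 − 0.45 × 12 = −3.3, or +3.3 with the arms exchanged.

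**Scale.** Assume SD 20, ICC 0.01, 3,000 patients per arm and 60% response. Mean respondents per unit are 0.60 × 6,000/40 = 90, and the design effect is 1 + 89 × 0.01 = 1.89. The standard error is 20 × √[1.89 × (1/1,800 + 1/1,800)] ≈ 0.92. A bias of 1.6 points would be about 1.6/0.92 ≈ 1.7 standard errors.

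**Simulation check.** The set-up was 40 clusters of 150, true effect zero and 400 runs. A baseline severity variable drove both outcome and response, more strongly for response in the control arm. Point estimates came from least squares with stratum and arm. Response averaged 64% / 55% and the gaps 1.5 / 4.4. The respondents-only estimate minus the all-patients estimate averaged −1.43 (Monte Carlo SE 0.02), and the formula gives the same −1.43. Adding the severity variable reduced the difference to 0.03 (Monte Carlo SE 0.02). The stratum-and-arm model thus does not correct selection by itself, and a measured baseline variable can do so when it is what drives response.

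**The case against.** **The method may exist elsewhere.** The protocol nowhere says that the primary analysis is restricted to respondents. A reader might infer such a rule from the model, but that inference rests on silence. SAP sections 2 and 6.4 both point to a Phase 1 SAP, where handling of missing SIS-16 would be expected. This stands as a limit on the finding. It does not remove the need for the protocol to state the method or cite it.

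**The trial works against non-response.** It would be wrong to say that the only answer is letters. Both arms have proxy response, the mailed SIS-16, $10 cash with the 80-day letter, a reminder magnet and several contact fields on the enrolment form. The protocol speaks of potential differences in loss, which is not a forecast of them. All this stands: these steps reduce non-response. They do not say what the analysis does with the scores still missing.

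**Covariates are already allowed.** The Analytical Plan names age, gender, race, stroke severity and SES for sensitivity analyses. Where baseline data explain response, an adjusted respondents-only model does much the same work as imputation from the same variables, as the simulation shows. This stands too, so imputation is not the only acceptable method. But these covariates are optional, outside the primary model, and not tied to missing outcomes.

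**The size is assumed.** A reader might go on to infer an inflated false-positive rate. Under the assumed SD and ICC above, biases of −0.4, −1.3 and −1.6 would move two-sided rejection from 5% to 7%, 29% and 42%. The documents do not support that as a finding. Those three cases all run against COMPASS, so the excess would nearly all be apparent harm. The two large figures also need a respondent gap that differs by arm, for which the documents offer no evidence.

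**Conclusion.** The concern holds in a limited form. The promised intention-to-treat population is wider than the group with a SIS-16 score, the primary model as written defaults to that group, and nothing supplied says how refusal, non-contact, withdrawal or death before day 90 is handled. Because one arm alone has extra contacts, this is more than a missing detail.

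Bias in the primary estimate is possible, not demonstrated. Neither its sign nor its size can be derived from the documents. The worked cases with 55–65% response and gaps of 6–12 points run from about −1.6 to +1.6 points, and the bias is zero when selection is the same in both arms. The gap should be closed for the primary endpoint. Confidence is medium, because the unseen Phase 1 SAP may already close it.

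**What to change.** 1. Define the primary SIS-16 analysis set as all enrolled, non-withdrawn patients. Say openly that this is narrower than all patients discharged home, and report withdrawals by arm.
2. State an explicit rule for deaths before day 90 (about 2%).
3. Handle missing SIS-16 with a method that uses baseline data already collected: multilevel multiple imputation with arm and hospital in the model, or an equivalent covariate-based method. Suitable predictors are NIHSS, aphasia, ambulatory status, discharge Rankin score and insurance from the enrolment data, and diagnosis from the eligibility form. Some of these can be recorded as not documented, and SAP 6.4 expects several important baseline characteristics to be missing in 5–10% of patients, so the predictors need imputing as well.
4. Report response by arm and by hospital, with the respondents-only model as a sensitivity analysis.
5. Add a tipping-point analysis that shifts non-respondents' scores separately by arm, because imputation cannot correct selection on the unobserved outcome.
6. If the Phase 1 SAP already specifies a method, align the protocol model with it and cite the section.

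The cost is wording and some extra programming, with no new data collection. Intervals may be somewhat wider.
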